6.7.3 Hospital transfers

Should a participant be transferred to another hospital prior to primary and secondary outcome data collection, their participation in the trial will be ongoing and the initial recruiting site will remain responsible for remote follow-up with participants and the receiving site (where necessary).

6.7.3 Estimands

Estimand component	Definition
Population	All participants meeting eligibility criteria and randomised to a treatment arm, with complete primary outcome data, and baseline data included in primary analysis model (i.e., complete case intention to treat population)
Treatment condition	Incentive spirometry in addition to usual care vs usual care without incentive spirometry, regardless of intervention compliance
Endpoint	Onset of new pulmonary complications within 5 days of randomisation (binary outcome)
Summary measure	Odds ratio
Handling of intercurrent events	Intercurrent events will be handled using a Treatment Policy approach (sensitivity analyses may be used to explore different approaches)

6.7.4 Target sample size (with calculation/justification)

276 patients recruited from 12 UK hospitals. The incidence of pulmonary complications in this population has been observed at 50% (5). In the only RCT of incentive spirometry for trauma identified, Sum and colleagues (8) observed a 50% absolute risk reduction in pulmonary complications, but this effect size was estimated with a large margin of error and may not be generalisable. A more conservative estimate of a 20% reduction in the intervention arm has, therefore, been proposed as a target effect size that is both achievable and meaningful to detect. Our PPI group agree this is a reasonable effect size to change practice. To detect a reduction in pulmonary complications from 50% in the control group to 30% in the intervention group with 90% power at a 5% alpha level, an analytical sample size of 248 is required. To allow for 10% attrition a total sample size of 276 is required. Most participants will remain inpatients at five days, and GP online records are routinely available for any that have been discharged. The only anticipated loss to primary outcome follow-up will be those who are admitted out of area and discharged within five days to another region where GP records may not be accessible. Sample size calculation was conducted using the 'power' command in Stata (version 18).

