6.7.2 Secondary outcomes

- Patient reported breathlessness at baseline and 5 (+2*) days (The Dyspnea-12 Questionnaire)
- Patient reported pain at baseline and 5 (+2*) days (Numeric Pain Rating Scale)
- Length of initial stay up to 30 days post randomisation
- Admission to Critical Care up to 30 days post randomisation
- Mortality up to 30 days post randomisation
- Hospital readmission within 30 days of randomisation

*Pain and breathlessness scores will be collected on day 5 where possible but a +2-day window will be accepted to accommodate lack of weekend staffing.

It is anticipated that the majority of patients will remain inpatients on day 5 and patient reported outcome measures can be collected in person by local site staff. For any patients discharged prior to day 5, follow-up can be completed remotely by telephone. The Dyspnea-12 questionnaire and Numeric Pain Rating Scale are both possible to complete by telephone. The researcher will make (up to) three contact attempts. If no response is received, the questionnaires will be marked as missing.

As the Dyspnea-12 Questionnaire includes a question pertaining to depressive symptoms, any participant identified as indicating severe levels of depression will be encouraged by local site staff to seek further evaluation or support from their treating clinician or General Practitioner.

The NPRS has been reported suitable to use with people with mild to moderate cognitive impairment (²⁴). We are unable to find a breathlessness patient reported outcome, suitable for trauma, that has been validated for cognitive impairment in this population. It is recognised that some data for this secondary outcome may be missing for those with mild to moderate cognitive impairment. However, “here and now” symptom self-reporting tools have been shown to be valid and reliable in persons with mild cognitive impairment in previous literature (²⁵) and use of the dyspnea-12 questionnaire in this

trial is supported by our patient and public involvement representatives. Secondary outcomes measured up to 30 days post randomisation will be collected by research staff from their hospital's electronic patient record.

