Once a participant has been randomised, they are enrolled in the study and treatment can proceed. Hospital (site/equivalent research) staff should proceed to complete and send a study approved letter to the participant’s GP (e.g. via post or secure email), including a copy of their patient’s completed consent form (or declaration form where appropriate), informing the GP that their patient has entered the trial; a copy of this letter should also be filed in the ISF.

Medical case notes containing source data or other trial-related information should also be identified by a label (or equivalent for electronic notes, where feasible), e.g. “Keep until at least dd/mm/yyyy” where the date given is at least five years after the end of the trial.

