7.9 Screening and Baseline Data Collection

A screening CRF will be completed for each participant that presents, meeting the inclusion criteria. Data capture on this CRF will include (but is not limited to):

- Age
- Sex
- Preferred language
- Eligibility criteria and confirmation of eligibility status
- Approach details and outcome (e.g. decline reasons)

During online randomisation, data capture will include eligibility criteria, mental capacity status, co-existing injury status (binary). During screening, patients' initials and year of birth will be recorded to ensure correct identification of patients at site.

Patient Reported Outcomes (participants): Site staff should endeavour to conduct patient reported outcome measures (PROMS) at the time of enrolment (consent). However, it is acknowledged that this may not be feasible, or appropriate, if e.g. the patient is fatigued or breathless following the consent discussion. As such, PROMS can be delayed but, like randomisation, should be completed within 24hours of being admitted to hospital. Participants will be asked to complete the PROMs according to how they feel at the time of completion. They may be completed with the assistance of a researcher/member of the clinical team (or person with caring responsibility, e.g. family member, if/where feasible).

CRF (site staff): A delegated site staff member will complete the Baseline CRF. Data capture on this CRF will include (but is not limited to):

- Patient name and contact details
- Patient demographics, including (confirmed) date of birth, ethnicity and gender
- GP (Practice) contact details
- Details of Personal Consultee/PLR (if relevant)
- Admission details
- Injury Details
- History of any chronic lung disease
- Pre-injury anticoagulant use
- Clinical observations
- Rockwood clinical frailty scale

- Intervention fidelity (provision of incentive spirometers to intervention participants only)

7.10 Data Collection at Day 5

Participants who remain in hospital at 5-days post-randomisation (+2 days):

A member of the site research team will ask these participants to complete the 5-day PROMs. These can be entered directly into the database by site staff or completed on paper CRFs downloaded from the study database by site staff for participants.

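### Out-of-area participants discharged before day 5 may be lost to the primary outcome although the trial has other routes to them; as only those event-free at discharge can go missing, complete-case absolute risks tend to be inflated

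*Protocol*

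**What the plan says.** **Source of the primary outcome.** Protocol 6.7.1 takes the outcome from inpatient records at five days. For participants who have already gone home, it adds a check of online GP records. It describes early discharges as few.

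**Accepted loss.** Section 6.7.4 allows 10% attrition and says who will be lost: "The only anticipated loss to primary outcome follow-up will be those who are admitted out of area and discharged within five days", where GP records in the other region may not be reachable.

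**Other contacts with the same people.** Section 6.7.2 says: "For any patients discharged prior to day 5, follow-up can be completed remotely by telephone". It allows up to three attempts, and section 7.10 (Data Collection at Day 5) repeats the remote follow-up with a +2-day window. Both serve the patient-reported outcomes only. The Baseline CRF in 7.9 records "GP (Practice) contact details". In 7.7 the instruction to "send a study approved letter to the participant" goes on to name that participant's GP as the addressee.

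**Analysis.** Section 6.7.3 (Estimands) limits the population to those "with complete primary outcome data", that is, complete cases. Section 11.1 reports an odds ratio, with the absolute difference and number needed to treat beside it. It promises an unspecified look at sensitivity to missing data.

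**The concern.** The trial telephones these participants about two secondary outcomes, and it knows and writes to their GP practice, but uses neither route to complete the primary outcome.

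The loss also depends on the outcome. The endpoint is one or more new complications within five days, so a single inpatient event settles it as present. Someone in this group who leaves hospital without an event has an unknown status until day 5. Only this second kind of participant can be missing. Complete-case analysis then removes people who are mostly non-events and leaves the events in.

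At stake are the absolute risks, the risk difference and the number needed to treat. If early event-free discharge differs between arms, the odds ratio is at stake too.

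**Working it through.** **1. The plan's own figure.** Inputs from 6.7.4: "To detect a reduction in pulmonary complications from 50% in the control group to 30% in the intervention group" and "with 90% power at a 5% alpha level, an analytical sample size of 248 is required". Allocation is 1:1 (6.2). Sidedness is not stated; two-sided is assumed.

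n per arm = [1.960·√(2·0.4·0.6) + 1.2816·√(0.5·0.5 + 0.3·0.7)]² / 0.20² = (1.3579 + 0.8692)² / 0.04 = 124.0, so 248 in all. Then 248/0.9 = 275.6, so 276. Both figures reproduce.

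**2. Complete-case risk.** Let
- p = true risk in the arm;
- a = share of the arm that is out of area, discharged early and without an accessible GP record;
- e = fraction of that group with an event before discharge (kept as events);
- f = fraction of that group whose first event comes after discharge (unseen).

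The share of the arm lost is a(1−e), and the unseen events are a·f. So

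observed risk = (p − a·f) / (1 − a(1−e)).

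The documents give none of a, e or f. I assume e = 0.10 and f = 0.05 and vary a. The observed risk exceeds p as long as f/(1−e), the later-event rate among those lost, is below p. Here that rate is 0.05/0.90 = 5.6%, against 50% and 30%.

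**3. Same share of each arm in the group** (truth: 50% v 30%, difference 20.0 points, NNT 5.0, odds ratio 0.429).

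| a | Control | Intervention | Difference | NNT | Odds ratio |
|---|---|---|---|---|---|
| 2% | 0.499/0.982 = 50.8% | 0.299/0.982 = 30.4% | 20.4 | 4.9 | 0.424 |
| 10% | 0.495/0.910 = 54.4% | 0.295/0.910 = 32.4% | 22.0 | 4.5 | 0.402 |

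The second row loses 9% of each arm, close to the whole 10% allowance. If exactly 10% of each arm is lost and all are true non-events, the risks are 0.50/0.90 = 55.6% and 0.30/0.90 = 33.3%.

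**4. When the odds ratio is and is not biased.** Take those lost as true non-events. If the same fraction of event-free participants is lost in each arm (one sixth, or 10% overall), the risks are 0.5/(0.5 + 0.5·5/6) = 54.5% and 0.3/(0.3 + 0.7·5/6) = 34.0%. The difference is 20.6 points and the odds ratio stays at 0.429.

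The odds ratio moves in step 3 because an equal share of each arm is a larger fraction of the control arm's non-events (50% of that arm) than of the intervention arm's (70%).

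**5. Unequal shares** (pure assumption, same e and f). With a = 1% of control and 3% of intervention, the odds ratio is (0.2985/0.6745)/(0.4995/0.4915) = 0.44. With 5% and 15%, the risks are 52.1% v 33.8%, the difference 18.3 points and the odds ratio 0.47.

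**The case against.** **The group is small.** Section 6.7.1 calls all early discharges few, and the out-of-area ones are a subset. At 2% of each arm the difference moves by 0.4 of a point. This stands: the 10% row is an upper bound, not an estimate.

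**The primary measure may be untouched.** The absolute difference and NNT are supplementary. A reader might infer that the loss hides benefit, because the device could bring forward event-free discharge. The documents do not support that: they give no discharge rates by arm, and the scenarios above move the difference both up and down. Only the conditional statement holds.

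**Coding is inferred.** A reader might infer that only event-free participants go missing and that everyone kept from this group is an event. Neither follows. Some of those lost may have an event between discharge and day 5, and some out-of-area records may be accessible after all. The protocol also does not say how an in-hospital event is coded when later records are missing; that it counts is read from the outcome definition.

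**Partly covered already.** Section 6.7.3 (Hospital transfers) gives the recruiting site remote follow-up duties, but only for transfers. The trial summary and 9.3.1 list GP records without restricting them to online access, so asking a practice is not barred; yet no section asks for it, and 6.7.4 accepts the loss. The sensitivity analysis in 11.1 cannot recover data never collected.

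**A telephone call is a weak source.** Most Table 2 components need imaging, blood gases or saturation readings, and participants are not blinded. This stands, and the call should not settle the outcome alone.

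**Conclusion.** The point holds as a worthwhile, inexpensive correction to data collection and to the complete-case rule. The protocol accepts a loss that can be reduced with contacts it already has, and that loss can fall only on participants event-free at discharge.

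The effect is on absolute risks, the risk difference and the NNT: from about 50.8% v 30.4% (2% of each arm) to about 54.4% v 32.4% (10%), instead of 50% v 30%. This rests on the assumed share of each arm, on 10% of the group having an event before discharge and 5% after it, and on in-hospital events being kept. Bias in the odds ratio is possible but needs a different fraction of event-free participants to be lost in each arm.

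A reader might also infer a shortfall in sample size or power, or a concentration of losses at Major Trauma Centres. Neither is supported. The 248 and 276 are correct and unaffected, power is already 90% at 248, and the protocol describes only a mix of sites.

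**What to change.** In 6.7.1 and 6.7.4, with matching wording in 6.7.3 (Estimands):

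- **(a)** State that a qualifying event in hospital counts as the primary outcome whatever the later access to records.
- **(b)** Where the GP record cannot be opened online, request the day 0–5 information from the GP practice already written to, and from any hospital attended. Use the existing day-5 call (with the consultee where capacity is lacking) only to identify antibiotics, chest diagnoses or attendances, which are then confirmed in records. The call is not a sole source for the outcome.
- **(c)** Do not simply drop those still undetermined. Include them by imputation that uses early-discharge status. Add a sensitivity analysis that treats participants event-free at discharge as non-events and then varies that assumption.

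The cost is a small number of GP requests, a few questions on a call that is already planned, and the related CRF and information-sheet wording. The sample size does not change.

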6.8 End of trial

Participants end their involvement with the trial when their last planned interaction with the study is complete (or efforts to complete this have been unsuccessful), or they have discontinued their participation in the study.

The end of trial will be when the last participant has completed their involvement with the trial, all data collection is complete and any data queries have been resolved, the database has been locked, and subsequent planned data analyses have been completed.

7 TRIAL PROCEDURES

7.1 Onboarding of participating sites

To ensure representativeness and generalisability of findings across different healthcare settings, participating sites will be purposively onboarded to include a balanced mix of Major Trauma Centres (MTCs) and Trauma Units (TUs). This approach allows the study to capture variations in patient populations, care delivery models, and resource availability across the trauma system. In addition, sites will be selected to achieve broad geographical coverage across urban, suburban, and rural areas, thereby reflecting the diversity of clinical practice and patient demographics across regions. Site selection will also take into account anticipated patient volumes, local research infrastructure, and competing study recruitment to support timely recruitment and study delivery.

7.2 Trial advertising

The trial will be promoted through targeted dissemination at national and regional Emergency Medicine and Physiotherapy conferences to raise awareness and support site engagement.

7.3 Screening and identification of participants

Hospital staff will be asked to complete a trial-specific screening Case Report Form (CRF) for each patient aged ≥ 65 years admitted to that hospital with acute rib fracture(s) following blunt chest wall trauma.

Recruitment will be undertaken 24 hours a day, 7 days a week. Potentially eligible participants will be identified by clinical staff or research delivery staff (e.g. Research Nurses/Physiotherapists) at the time of arrival in ED or on/after transfer to inpatient settings (e.g. ward, acute medical/surgical assessment unit). Upon identifying a (potentially) eligible patient, a member of the clinical team or research practitioner will give the patient the written study Summary Participant Information Sheet (Summary PIS) and, where appropriate, the full Participant Information Sheet (Detailed PIS) (e.g. the patient has read the Summary PIS and requested further information and/or is suitably comfortable and able to read both documents at that time). We recognise that our target population is older adults. Patient information materials will therefore be available in a variety of formats, including paper (normal and large print) and video, as advised by our patient groups to maximise participation across all potentially eligible patients.

Patients will be given sufficient time to read/view the information material and ask any questions they may have about the trial. The length of time patients will have to consider participation will vary due to the nature of EDs and assessment pathways. If appropriate, consent can be received whilst the patient is still within the ED, however consent will not be taken until immediate care needs have been addressed. When considering participation in the emergency setting, patient consideration-time is estimated to be from one to four hours; this approach is considered acceptable by patients, as demonstrated by other ED-based research undertaken by our group (^{5,26}). If required, the participant can be given longer to consider involvement even if transferred to a ward. However, due to the need for early intervention, a maximum of 24 hours from admission to randomisation will be set (and written consent must be received prior to randomisation).

In patients without capacity, we will seek approval from a patient's personal consultee/legal representative (see section 7.6)

Eligibility is required to be confirmed by a member of the team who has been delegated this role and is trained in the trial.

7.4 Inclusivity

The NIHR INCLUDE guidance (27) has been used to inform study design and assess potential barriers to inclusion, ensuring consideration of under-served groups throughout the research planning process. This study will recruit participants from a geographically diverse range of research sites across the UK, including urban, rural, and socioeconomically varied areas. This approach is designed to ensure that the study population reflects the broad demographic and health system contexts in which the intervention may ultimately be used.

All patients who meet the eligibility criteria will be offered the opportunity to participate, and no exclusions will be made on the basis of characteristics such as sex, gender identity, ethnicity, socioeconomic status, or frailty unless scientifically justified. Local recruitment teams will be supported with materials and strategies to enable inclusive recruitment, and screening logs will be used to monitor uptake and identify any barriers to participation.

Efforts will be made to identify and minimise barriers to participation among under-served or marginalised groups, including accessible study materials (e.g. large print font) and engagement with local community or patient groups where appropriate.

7.5 Consent

Written informed consent must be obtained before any trial related procedures or assessments can be undertaken. Patients who are willing and eligible to participate in the study will be asked to provide written informed consent and they will be allocated a unique study identification (I.D) number. Ideally patients will have read both the Summary PIS and Detailed PIS before providing written informed consent. We recognise, however, that it may not be appropriate or feasible for some patients to read both documents, or at least not the Detailed PIS in full, prior to providing written informed consent (e.g. due to being in pain, frailty, visual impairment). In these circumstances, patients who have read (or discussed) the Summary PIS, or watched the video PIS, and are willing and eligible to participate will be asked to provide full (written) informed consent and will be asked to read (or discuss) the Detailed PIS in full as soon as they are able.

The written informed consent process will be undertaken by an appropriately trained clinician or member of the research team. All members of the clinical and/or research team delegated by the PI to undertake the consent procedure must be listed on the study delegation log at the relevant site. These individuals should all understand the protocol and the potential implications it may have on the people to be involved; understand alternative treatments available to potential participants; have an ability to communicate effectively with potential participants, including explaining complex scientific/medical concepts; and appreciate how to optimise the voluntary nature of decision making, avoiding undue influence.

Besides completing the consent form (which includes the study title and date of consent), sites should record key details of the informed consent process in the patient's medical notes. Copies of the consent form should be issued to the participant and stored in the medical notes. A scanned copy will also be uploaded to the study database. The original should be filed locally in the site's physical site working folder.

NB: When a patient has capacity but is unable to indicate their consent by signing/mark a Consent Form; then they may give their informed consent verbally in the presence of a witness (any clinician

on duty, nurse or doctor) *in addition to* the staff member taking consent. The witness will also be asked to countersign the consent form.

For patients lacking capacity to consent, recruitment can still be considered if a personal consultee/Personal Legal Representative (PLR) is available, and it is deemed that the patient will manage to use the incentive spirometer with their supervision/support (approach supported by PPI) (see section 7.6)

Where patients provide informed consent but endure a loss of capacity for ≥48 hours during the study, a personal consultee/PLR will be given the Summary Patient Information Sheet and/or equivalent video with the Detailed Information Sheet, and approached to provide approval for continued participation via a Consultee Declaration/PLR AWI Consent form. If a Consultee/PLR is not available, is unwilling or advises that the participant should no longer take part in the study after they have lost capacity, then their participation will stop; however, data already collected up to the point of loss of capacity will be retained and analysed. Advice from a Consultee/PLR about whether the individual would wish to be included in the study will be obtained in the same way as described above. Patients will be informed of this process at the outset via the participant study information materials. In all cases, we will consult with carers and take note of any signs of objection or distress from the participant, and we will withdraw a participant if they raise objections.

Informed consent/consultee approval will endure unless the individual requests to change permissions/withdraw, in which case the relevant procedures will be followed; see section 7.10.

It is possible that patients may regain capacity after a Consultee/PLR has agreed to them remaining in the study. In this case, we consider the original consent to remain valid. Staff will update the patient of any ongoing study procedures, and the patient will retain the right to withdraw at any time.

7.6 Patients with mild to moderate cognitive impairment lacking capacity to provide consent for themselves

Including patients with mild to moderate cognitive impairment is essential. It is widely agreed that such persons have a higher risk of falls, a common cause of rib fractures (²⁸). Cognitive impairment in this population may stem from a chronic neurodegenerative condition, such as Alzheimer's disease, which is likely to persist for the duration of the trial. These individuals are frequently considered unsuitable for more invasive treatments due to frailty, multiple comorbidities, or impaired capacity to make informed decisions.

There is growing recognition that older adults tend to under-report pain; however, many studies have overlooked cognitive impairment as a confounding factor in pain assessment (²⁴). In some cases, cognitive impairment may not be permanent — for example, when caused by an acute medical issue such as delirium. In these scenarios, cognitive function may improve over time, highlighting the importance of considering both chronic and temporary forms of impairment when evaluating this patient group

It is important to evaluate supportive interventions like the incentive spirometer in these vulnerable groups. The incentive spirometer is non-invasive, safe, and simple to use — qualities underscored by its routine application in paediatric populations. Its feasibility in older adults with cognitive impairment warrants further investigation, especially as they may benefit from interventions that are low risk and do not rely on complex instructions or decision-making capacity.

All senior ED clinicians and research practitioners have training in capacity assessment. Where, upon the initial capacity assessment, patients are judged to be unable to provide informed consent for themselves at the time a decision or action needs to be taken (under some circumstances, loss of capacity may be due to stress or pain related to their traumatic injuries) a personal consultee/Personal Legal Representative will be approached for approval.

In England, Wales and Northern Ireland a personal consultee will be presented with the Summary Participant Information Sheet or equivalent video and, where appropriate, the Detailed PIS. Based on the study information, the Consultee will provide advice about whether the individual would wish to be included in the study or not. A patient will only be enrolled via personal consultee approval if the consultee is available to provide approval within 24 hours of the patient's admission to hospital and reasonable support with IS training/use.

In Scotland a Personal Legal Representative (PLR) will be approached and presented with the Personal Legal Representative Summary PIS or equivalent video, and supporting Detailed PIS, and will provide advice about whether the individual would wish to be included in the study or not. A Personal Legal Representative can be a Welfare Guardian or Welfare Attorney, or the patient's nearest relative. If a PLR is not available, the participant will not be enrolled.

Patients where capacity is regained within 5 days of randomisation: patient's who have regained capacity (confirmed as ≥ 48 hours) will be approached by a member of the research team and provided with information about the study that will explain what has (likely) happened so far. If day 5 post-randomisation falls on a weekend, assessment will be completed on the following working day. Patients will be asked to provide consent to continue in the study; they may wish to continue active involvement in the study (e.g. will complete questionnaires) or passive involvement (e.g. no questionnaires but allow continued access to medical records only). If a patient decides that they do not wish to continue in the study, their ongoing participation will stop; however, data collected up to this point will be retained and analysed.

It is possible that patients may lose capacity again, after agreeing to remain in the study. In this case, we will consider the original consultee/PLR consent to remain valid. Staff will inform the consultee/PLR, who will retain the right to withdraw the person they provided consent for at any time.

A summary of the various study invitation and consent pathways and documentation are shown in Figure 1 below.

[figure not shown]
[figure not shown]

Figure 1: Approach and consent pathways

